10.3 Reporting Requirements

Any AE considered Serious by the local Investigator, or which meets the previous SAE criteria must be reported to Central Data Management Unit (CDMU) /QCGC Research and reviewing HREC according to local HREC policy.

The following must occur within 24 hours from the time that the site personnel first become aware of the serious adverse event:

The site personnel must complete the SAE case report form and submit this to the Lead Site/ CDMU below:

| |
|------------------------------------------------------------------------------------------------------------------------------------------------------------------------------------------|
| ANVU Trial Manager |
| Queensland Centre for Gynaecological Cancer (QCGC) Research [name] Email: [contact] |

As well as providing the SAE form to CDMU the site is also required to email a brief notification of SAE data transmission. All SAE's will be reported by the CDMU to a central HREC according to central HREC policy and the Independent Data Safety Monitoring Committee (IDSMC).

SAEs will be categorised using the CTCAE V5.0 and collected for 6 months after surgery.

10.4 Time Period, Frequency, Method of Detecting AEs, and SAEs

All AEs will be recorded between the time of surgery and the 12-month follow-up visit and SAEs will be recorded up to 6 months after surgery.

Each participant will be monitored regularly by the investigator and study personnel for AEs occurring throughout the study. The investigator or designee will enquire about AEs and SAEs by asking a non-leading question, for example:

“How are you feeling?”

At subsequent scheduled intervals participants will be asked:

“Since you were last asked, have you felt unwell or different from usual?”

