10.1 Definition of an Adverse Event (AE)

An AE is any untoward medical occurrence in a patient, which does not necessarily have a causal relationship with this treatment. AE will be categorised using the CTCAE V5.0 and be collected for 12 months after surgery. An AE can be any unfavourable and unintended sign (including an abnormal laboratory finding), symptom, or disease (new or exacerbated) temporally associated with the use of a medicinal product, whether or not considered related to the medicinal product. For marketed medicinal products, this also includes failure to produce benefits (i.e. lack of efficacy), abuse or misuse.

Examples of an AE include:

- Exacerbation of a chronic or intermittent pre-existing condition including either an increase in frequency and/or intensity of the condition.
- New conditions detected or diagnosed after investigational product administration even though it may have been present prior to the start of the study.
- Signs, symptoms, or the clinical sequelae of a suspected interaction.
- Signs, symptoms, or the clinical sequelae of a suspected overdose of either investigational product or a concurrent medication (overdose per se should not be reported as an AE/SAE).
- Pre- or post-treatment events that occur as a result of protocol-mandated procedures (i.e. invasive procedures, modification of participants' previous therapeutic regimen).

Examples of an AE do not include:

- Medical or surgical procedures (e.g. endoscopy, appendectomy); the condition that leads to the procedure is an AE.

- Situations where an untoward medical occurrence did not occur (social and/or convenience admission to hospital).

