SAEs will be categorised using the CTCAEs V5.0 and be collected for 6 months after surgery.

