11.2.3 Morbidity of Intervention

Post-surgery, patients will be assessed daily until discharge from hospital. Perioperative outcomes including duration of surgery (time from skin incision to wound closure), length of hospital stay,

estimated intraoperative blood loss, requirements for blood transfusions, intraoperative complications, and crossovers (including the clinical necessity for a comprehensive LND) will be recorded. Intraoperative injuries, postoperative AEs and SAEs will be recorded according to the CTCAE V5.0, at predefined time points for up to 12 months. We will compare the incidence of (a) intraoperative; (b) postoperative; and (c) serious AEs at 8 weeks and 6 months and 12 months post-surgery.

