| | SCREENING/ ELIGIBILITY | T0 BASELINE | T1 WEEK8 | T2 FOLLOW UP (MONTH 3) | T3 FOLLOW UP (MONTH 4) | T4 FOLLOW UP (MONTH 6) | T5 FOLLOW UP (MONTH 8) | T6 FOLLOW UP (MONTH 9) | T7 FOLLOW UP (MONTH 10) | T8 FOLLOW UP (MONTH 12) |
|------------------------------------------------------------------------------------------------------------------------------------------|----------------------------|----------------|-------------|------------------------------|------------------------------|------------------------------|------------------------------|------------------------------|-------------------------------|-------------------------------|
| a) US Suspicious/ Indeterminate: SNB/IFL | | x | | | | | | | | |
| b) Negative Groin Ultrasound: Randomisation To Upfront Groin LND OR 2 Monthly Groin USM + 3 Monthly Physical Examination | | x | | | | | | | | |
| Surgical Excision of The Primary Tumour - Planned Surgery | | x | | | | | | | | |
| Central Histopathology Review | | x | | | | | | | | |
| Groin USM (Interventional Treatment) | | | x | | x | x | x | | x | x |
| Current Medications | | x | x | | x | x | x | | x | x |
| Adverse Events | | | x | | x | x | x | | x | x |
| Hospitalisations | | | x | | x | x | x | | x | x |
| Serious Adverse Events | | | x | | x | x | | | | |
| Physical Examination (Interventional Treatment) | | | x | x | | x | | x | | x |
| Disease Status | | | x | | x | x | x | | x | x |
| PROMS & HRQL | FACT-V | | x | x | | x | | | | x |
| | EuroQol-5D (EQ-5D) | | x | x | | x | | | | x |
| | Lymphoedema Assessment | | x | x | | x | | | | x |
| | Fear of Recurrence (FCR-4) | | | | | | | | | x |

17. References

1. Kim, C.H., et al., *Pathologic ultrastaging improves micrometastasis detection in sentinel lymph nodes during endometrial cancer staging*. *Int J Gynecol Cancer*, 2013. 23(5): p. 964-70.
2. *Vulvar cancer statistics*. 2022 [cited 2023; Available from: <https://www.canceraustralia.gov.au/cancer-types/vulval-cancer/statistics>].
3. *6 National Health Priority Areas (The Burden of Disease and Injury in Australia)*. [cited 2023; Available from: <https://www.aihw.gov.au/getmedia/78bc02fd-a75e-4f25-a0ae-b27f7bb2a4b2/bdia-c06.pdf.aspx>].
4. NF, H. and E. PJ, *Vulvar Cancer*. Practical Gynecologic Oncology. 2021: Walters Kluwer.
5. Hoskins, W.J., *Principles and Practice of Gynecologic Oncology*. 2005: Lippincott Williams & Wilkins.

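### SAE collection stops at 6 months in section 10 and the study schedule, but section 11.2.3 records and compares SAEs to 12 months

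*Protocol*

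**What the plan says.** Six months, in the parts of the protocol that sites work from:

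- Section 10.2: "SAEs will be categorised using the CTCAEs V5.0 and be collected for 6 months after surgery".
- Section 10.3: "SAEs will be categorised using the CTCAE V5.0 and collected for 6 months after surgery".
- Section 10.4: "SAEs will be recorded up to 6 months after surgery".
- Section 16, study schedule: the row "Serious Adverse Events | | | x | | x | x" marks week 8, month 4 and month 6, and is blank afterwards.
- Section 7.5: SAE collection is listed at week 8, month 4 and month 6. The lists for months 8, 10 and 12 contain no such item.

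Twelve months, in the analysis section:

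- Section 11.2.3: "postoperative AEs and SAEs will be recorded according to the CTCAE V5.0, at predefined time points for up to 12 months", followed by a comparison of "serious AEs at 8 weeks and 6 months and 12 months post-surgery".

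The window for adverse events in general is not in dispute. Section 10.1 says "AE will be categorised using the CTCAE V5.0 and be collected for 12 months after surgery", and section 10.4 says "All AEs will be recorded between the time of surgery and the 12-month follow-up visit".

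**The concern.** The trial withholds a standard operation from the ultrasound monitoring (USM) arm, and section 12.1 names undetected groin recurrence, possibly leading to death, as the main risk. Morbidity at 12 months is a secondary endpoint (section 5.6), and the SAE comparison in section 11.2.3 is one component of it.

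Two things are at stake if the 6-month rule is the one applied. The 12-month SAE comparison has no data for the second half of follow-up. And section 10.3, which sends SAEs within 24 hours to the central data unit and from there to the ethics committee and the IDSMC, has no SAE collection feeding it after month 6.

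The timing also matters by arm. In the dissection arm, the groin lymph node dissection (LND) takes place at the start. In the USM arm, section 7.5 allows a change on any later scan to lead to LND.

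**Working it through.** No sample-size or power formula applies; the check is a comparison of the stated windows.

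**1. The two windows**

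| Item | Sections 7.5, 10.2–10.4 and 16 | Section 11.2.3 |
|---|---|---|
| New SAEs recorded until | month 6 | month 12 |
| Visits with an SAE item | 3 (week 8, months 4 and 6) | not listed |
| Share of follow-up covered | 6 of 12 months | 12 of 12 months |
| SAE comparison at 12 months | no data after month 6 | planned |

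A cumulative SAE incidence at 12 months cannot be obtained from events collected to month 6. Section 10.6.4 follows events to 30 days after the 12-month visit, but that concerns events already documented and does not open collection of new ones.

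**2. Where the USM scans fall**

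Postoperative scans are at week 8 and months 4, 6, 8, 10 and 12, six in all. Those at months 8, 10 and 12 come after the cut-off: 3 of 6. An LND prompted by the month-6 scan would also take place after SAE collection had closed. The month-12 scan lies at the end of the longer window as well, so collection to month 12 would catch little of what follows from that scan.

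**3. Would such events be SAEs?**

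Some plausibly would. Section 10.2 counts admission to hospital and gives malignancy as an example of an important medical event. Its exemption for elective admission covers only a condition that has not worsened since baseline. However, section 10.1 says that a surgical procedure is not itself an AE; the condition behind it is. Women having a delayed LND are therefore not the same count as SAEs.

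**4. Can the number be derived?**

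No. The pilot (section 3.4) reports that its positive nodes appeared within 12 months, without a split around month 6. For illustration only, assume that 25% to 75% fall after month 6, with 120 USM women:

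- Node-positive at the pilot rate: 120 × 3/32 = 11.25; after month 6, 2.8 to 8.4.
- Groin recurrence at the anticipated 3% (section 11.1): 120 × 0.03 = 3.6; after month 6, 0.9 to 2.7.
- Groin recurrence at the 6% limit: 120 × 0.06 = 7.2; after month 6, 1.8 to 5.4.

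These are women with nodal disease or recurrence, not SAEs, and the recurrences are counted by the primary endpoint whatever the SAE window.

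**5. What does not depend on the SAE window**

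The stopping rule and the declaration of safety in section 11.1 use groin recurrence only. With the stated boundaries and a true rate of 3%, exact binomial recursion gives a probability of 0.018 of stopping for safety (stated: below 2%). It gives 0.847 for declaring safety if 5 or fewer of 120 qualifies (stated: 0.85). Changing the SAE window alters neither figure.

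**The case against.** The strongest reply is that late events are recorded by other routes. AEs are graded and assessed for outcome and relationship to treatment up to month 12. Hospitalisations and disease status are collected at months 8, 10 and 12. Women who have a delayed LND stay in data collection (section 6.5.3), and recurrence and death enter disease-free and overall survival. Palpable groin recurrence is monitored continuously in all groups (section 12.1). The opening of section 10 also states the 24-hour duty without a time limit.

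Most of this stands, and it rules out three stronger readings that a reader might infer:

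- *Late serious harm is neither reported nor counted.* Not supported. The events are recorded. What is lost is their classification as serious, expedited reporting and the 12-month SAE comparison.
- *The safety committee would not learn of late groin recurrence.* Not supported. That event has its own monitoring under sections 11.1, 12.1 and 12.4, with no 6-month limit.
- *The SAE comparison is biased in favour of USM.* Possible, but not shown. The cut-off is the same for every group, and sections 3.1 and 3.3 describe long-term morbidity after LND, so late serious complications in that arm would be missed too.

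The other records do not fully replace SAE data. Section 10.6.1 itself warns that a severe event is not the same as a serious one, so grade does not give seriousness. Hospitalisation is only one of the criteria in section 10.2. And an untimed 24-hour duty is weak protection when the same section limits collection to 6 months and the later visits do not ask for SAEs.

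**Conclusion.** The point holds as an internal contradiction. Three statements in section 10, the schedule and the visit lists set a 6-month SAE window; section 11.2.3 sets 12 months and plans an analysis on it. If sites follow section 10 and the schedule, which is the likely outcome because those govern their work, half of follow-up has no new SAE collection and the 12-month SAE comparison cannot be carried out as written.

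The gap may affect the arms unequally, because LND can come late in the USM arm. The number of SAEs missed and the net direction cannot be derived from the protocol; the ranges above rest on an assumed timing and count women with nodal disease or recurrence. The consequence is confined to safety reporting after month 6 and one component of a secondary endpoint. The primary endpoint, the stopping rule and the declaration of safety are not affected.

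**What to change.** Bring sections 10.2, 10.3, 10.4 and 16 into line with section 11.2.3 by collecting and reporting SAEs to the month-12 visit in all groups, and add an SAE item to the visit lists for months 8, 10 and 12. SAE visits rise from 3 to 6, and the 12-month comparison can then be made as planned.

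The cost is a protocol amendment and some extra SAE forms. The added burden is small, because those three visits already record AEs and hospitalisations. No sample-size or power figure changes.

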10.5 Recording of AEs and SAEs

When an AE/SAE occurs, it is the responsibility of the investigator or designee to review all documentation (e.g. hospital progress notes, laboratory, and diagnostic reports) relative to the event. The investigator or designee will then record all relevant information regarding an AE/SAE into the CRF/eCRF.

It is not acceptable for the investigator to send photocopies of the participant's medical records to QCGC Research in lieu of completion of the appropriate AE/SAE CRF/eCRF pages. However, there may be instances when copies of medical records for certain cases are requested by QCGC Research. In this instance, all participant identifiers will be blinded on the copies of the medical records prior to submission to QCGC Research.

For each AE, start and stop dates, action taken, outcome, severity, and relationship to study treatment/intervention must be documented. If an AE changes in frequency or intensity during a study, a new entry of the event must be made in the CRF/eCRF.

The investigator will attempt to establish a diagnosis of the event based on signs, symptoms, and/or other clinical information. In the absence of a diagnosis, the individual signs/symptoms should be documented.

All details of any treatments initiated due to the adverse event should be recorded in the participant's notes and the CRF/eCRF.

10.6 Evaluating AEs and SAEs

10.6.1 Assessment of Severity

The investigator or designee will assess intensity for each AE and SAE reported during the study. The assessment will be based on the investigators or designee's clinical judgement.

Intensity of adverse events will be graded using the National Cancer Institute CTCAE V5.0 and reported in detail as indicated on the CRF/eCRF.

If an adverse event occurs which is not contained in the CTCAE V5.0, the five-point scale below will be used:

- Mild: An event that is easily tolerated by the participant, causing minimal discomfort, and not interfering with everyday activities
- Moderate: An event that is sufficiently discomforting to interfere with normal everyday activities
- Severe: An event which is incapacitating and prevents normal everyday activities
- Life Threatening: represents an immediate threat to life
- Death

An AE that is assessed as severe should not be confused with a SAE. Severity is a category utilised for rating the intensity of an event; and both AEs and SAEs can be assessed as severe. An event is defined as "serious" when it meets one of the predefined outcomes as described in section 10.1 "Definition of an SAE".

10.6.2 Assessment of Causality

The investigator or designee is obligated to assess the relationship between treatment and the occurrence of each AE/SAE. They will use clinical judgment to determine the relationship. Alternative causes, such as natural history of the underlying diseases, concomitant therapy, other risk factors, and the temporal relationship of the event to the treatment will be considered and investigated.

The causal relationship to the treatment assessed by the Investigator or designee should be assessed using the following classifications:

- Not Related: In the Investigator's opinion, there is not a causal relationship between the study treatment and the adverse event
- Unlikely: The temporal association between the AE and study treatment is such that the study treatment is not likely to have any reasonable association with the AE
- Possibly: The adverse event could have been caused by the study participant's clinical state or the study treatment
- Probably: The AE follows a reasonable temporal sequence from the time of study treatment administration, abates upon discontinuation of the study treatment and cannot be reasonably explained by the known characteristics of the study participant's clinical state
- Definitely: The AE follows a reasonable temporal sequence from the time of study treatment

There may be situations when an SAE has occurred, and the investigator has minimal information to include in the initial report to QCGC Research. However, it is very important that the investigator always assesses causality for every event prior to transmission of the SAE form to QCGC Research. The investigator may change her/his opinion of causality in light of follow-up information, amending the SAE form accordingly. The causality assessment is one of the criteria used when determining regulatory reporting requirements.

10.6.3 Exemptions from AE/SAE Reporting

Clinical Laboratory Abnormalities and Other Abnormal Assessments as AEs and SAEs:

Laboratory test value abnormalities will not be reported as AEs, unless there is an associated clinical condition for which the participant is given treatment, concomitant treatment is altered, or the event is considered a serious adverse event.

The investigator or designee will exercise their medical and scientific judgement in deciding whether abnormal laboratory findings, or other abnormal assessment is clinically significant.

10.6.4 Follow-Up of AEs and SAEs

After the initial AE/SAE report, the investigator or designee is required to proactively follow each participant and provide further information to QCGC Research on the participant's condition.

All AEs and SAEs documented at a previous visit/contact and are designated as ongoing, will be reviewed at subsequent visits/contacts.

All AEs and SAEs will be followed until resolution, until the condition stabilises, until the event is otherwise explained, until the participant is lost to follow-up, or 30 days post 12 month follow up visit. Once resolved, the appropriate AE/SAE CRF/eCRF page(s) will be updated. The investigator will ensure that follow-up includes any supplemental investigations as may be indicated to elucidate the nature and/or causality of the AE or SAE. This may include additional laboratory tests or investigations, histopathological examinations, or consultation with other health care professionals.

New or updated information for SAEs will be recorded on the originally completed SAE form, with all changes signed and dated by the investigator or designee. The updated SAE form should be resent to QCGC Research.

10.6.5 Safety Monitoring

QCGC Research will provide safety information to the Trial Management Committee (TMC) and the Independent Data Safety Monitoring Committee (IDSMC) on a periodic basis for review.

Trial safety data will be monitored to identify:

- new adverse reactions to the trial treatment regimen or individual trial treatments
- SAEs
- trial related events that are not considered related to the trial treatment regimen.

Should QCGC Research identify or suspect any issues concerning participant safety at any point throughout the trial, the Chief Investigator (CI) or TMC will be consulted for their opinion.

10.6.5.1 Evaluating and Reporting Positive Nodes

The senior medical imaging specialists will review the serial high-resolution bilateral ultrasound scans, evaluating for the presence of positive lymph nodes or any suspicious findings, relying on their clinical expertise. Radiologists will send their report to the local PI within 5 working days of ultrasound completion. All sites are required to enter the completed ultrasound eCRF on REDCap within 5 working days of ultrasound completion. Additionally, they must upload a copy of a signed and de-identified ultrasound report to REDCap, where QCGC Research will verify ultrasound completion. All sites should also provide a copy of de-identified US images to QCGC Research through The University of Queensland Research Data Manager platform (UQRDM) for quality assurance purposes. UQRDM is a secure platform designed for storing, managing, and sharing research data. It ensures compliance with data protection regulations and facilitates efficient data access and collaboration among researchers.

As explicitly stated in section [6.5.3](#) of the protocol, if suspicious, indeterminate, or positive nodes or any other concerning indicators are detected, the participant will be referred to either the local PI or the specialist gynaecological oncologist to discuss their options. Depending on the clinical judgment of the clinician, the participant may be recommended for LND (standard treatment) or may opt to continue with bilateral groin USM every two months and clinical examinations every three months (remaining on trial).

Participants receiving interventional treatment (serial groin USM in conjunction with clinical examination) who develop suspicious, indeterminate, or positive nodes are not removed from the trial as we still collect their data. The requirement for bi-monthly bilateral ultrasound, physical examination and blood tests will be discontinued.

11. Statistical Considerations

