An overall assessment will be made by the radiologist into normal or suspicious/positive. Radiologists will send their report to the local PI within 5 working days of ultrasound completion. All sites are required to enter the completed ultrasound eCRF on REDCap within 5 working days of ultrasound completion. Additionally, they must upload a copy of a signed and de-identified ultrasound report to REDCap, where QCGC Research will verify ultrasound completion.

If the participant is randomised to serial groin USM, patients will have surgical excision of the primary vulvar tumour followed by bilateral groin ultrasound every two months and clinical examinations every three months for the 12 months.

If suspicious, indeterminate, or positive nodes or any other concerning indicators are detected, the participant will be referred to either the local PI or the specialist gynaecological oncologist to discuss their options. Depending on the clinical judgment of the clinician, the participant may be recommended for LND (standard treatment) or may opt to continue with bilateral groin ultrasound every two months and clinical examinations every three months (remaining on trial). Participants undergoing LND will no longer need bilateral groin ultrasound and blood collections every two months and clinical examinations every three months. However, their data will still be collected up to the original 12-month point. Data collected will include documentation of the status of disease, AEs, pain level, health status and quality of life and lymphoedema. Please refer to section [10.6.5.1](#), titled 'Evaluating and Reporting Positive Nodes', for further information.

Patients that fail to comply with the serial ultrasound and clinical examination schedule will be removed from the trial and referred back to their gynaecological oncologist for alternative treatment for safety reasons.

7. Project Methodology

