7.5.2. Postoperative Month 3 ± 7 days (Visit 5) - Interventional Arm

Evaluate symptoms and conduct a physical examination in alignment with ESMO guidelines (interventional treatment):

To mitigate the likelihood of participants experiencing unfavourable outcomes, we have implemented precautionary measures. Participants in the interventional arm are required to have clinical examinations every three months following surgery to remove the primary vulvar tumour. This requirement persists for a duration of 12 months. Ideally, participants will be scheduled to undergo their physical examination on-site. However, for those who reside far away and cannot return every three months, they can alternatively arrange an appointment with their local gynaecologist. A signed and de-identified visit report must be uploaded to REDCap within 5 working days, where QCGC Research will verify the completion of the clinical examination.

If any concerning indicators are detected, the participant will be referred to either the local PI or the specialist gynaecological oncologist to discuss their options. Depending on the clinical judgment of the clinician, the participant may be recommended for LND (standard treatment) or may opt to continue with bilateral groin ultrasound every two months and clinical examinations every three months (remaining on trial). Participants undergoing LND will no longer need bilateral groin ultrasound and blood collections every two months and clinical examinations every three months. However, their data will still be collected up to the original 12-month point. Data collected will include documentation of the status of disease, AEs, pain level, health status, quality of life, and lymphoedema.

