12.1 Patient Safety

The number of enlarged, palpable groin node metastases/recurrences in all three groups will be monitored continuously and trial stopping rules are in place if these numbers exceed the upper limit of normal. Ultrasound is non-invasive and does not use radiation. In Australia, all ultrasound scans will be performed by registered sonographers with a postgraduate degree recognised by the Australian Sonographers Accreditation Registry (ASAR) and monitored by the TMC. At International sites, all ultrasound scans will be performed by sonographers with equivalent credentials. Blood tests will be performed up to 30 days prior to surgery (as part of routine blood tests), 8 weeks post-operation and then every 2 months for ultrasound patients. The risk of participants in having the intervention is to develop a clinically apparent groin node recurrence that would grow to a large size undetected and that would lead to poor survival outcomes (potentially leading to death). To mitigate this risk, we have implemented precautionary measures. Following surgery to remove the primary vulvar tumour, participants in the intervention group will have a groin ultrasound scan every 2 months and a clinical examination every 3 months, for a period of 12 months. Eligibility for participation in this study requires a commitment from patients to adhere to these frequent follow-up intervals and only participants with a normal/negative baseline groin node ultrasound are eligible to be randomised.

The prospective study's design, stringent inclusion and exclusion criteria, a well-defined follow-up schedule involving bi-monthly ultrasounds and clinical examinations every three months, use of a synoptic reporting format for groin ultrasound findings and the appropriate allocation of resources, including dedicated study staff, along with the comprehensive training of sonographers will effectively reduce the likelihood of participants experiencing unfavourable outcomes. However, it's important to mention that even when patients undergo groin node dissection (LND) as part of their standard treatment, the risk of subsequent groin node metastasis and the associated risk of death fall within the range of 3% to 10%, as indicated in published literature [6].

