12.7 Missing Ultrasound or Physical Examination

If a participant allocated to the interventional group misses their ultrasound appointment or physical examination by ± 7 days, both the trial PI and the site will be notified. The PI will investigate, with trial management assisting in promptly rescheduling the ultrasound appointment or physical examination within 7 days. Actions will be implemented to mitigate the risk, which may include the possibility of removing the patient from the trial.

We will allocate dedicated staff to ensure participants adhere to and comply with all study monitoring schedules, ensuring ultrasound scan appointments or physical examinations are conducted within a ± 7 -day window, and that all eCRFs and reports are promptly received. Should any issues arise, the site PI will be immediately informed.

13. Dissemination of Findings

We expect the results of this study will be disseminated by publication in a peer reviewed journal, presentation at national or international conferences, and circulation throughout patient and professional organisations relevant to gynaecological oncology care. The investigators agree that publications or presentations of any of the results from the study will take into account the co-operative nature of the conduct of the study and the overall objective of increasing public knowledge and shall be in accordance with accepted scientific practice, academic standards and customs and in accordance with the protocol and with any more specific publication/presentation guidelines developed by the trial management committee during the course of the study, including but not limited to the following:

As the study is a multi-centre study, any results from a single centre must not be published before the publication of results from all centres and before the trial PI does not give explicit written permission to the site/investigator to do so.

Individuals making a substantial contribution to the study will be recognised with co-authorship in publications from the study unless they elect not to be recognised.

14. Ethical Consideration

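### Section 10.6.5.1 ends mandatory groin surveillance for every ultrasound-arm woman with an abnormal node, whereas 6.5.3 and 7.5.2 release only those who undergo lymph node dissection

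*Protocol*

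**What the plan says.** Section 10.6.5.1 first restates the rule of section 6.5.3. A USM participant with a suspicious, indeterminate or positive node is referred to the local PI or a specialist gynaecological oncologist. She may then be recommended for LND, or she "may opt to continue with bilateral groin USM every two months and clinical examinations every three months (remaining on trial").

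The closing paragraph of 10.6.5.1 then speaks of USM participants "who develop suspicious, indeterminate, or positive nodes are not removed from the trial as we still collect their data", and adds: "The requirement for bi-monthly bilateral ultrasound, physical examination and blood tests will be discontinued". LND is not mentioned in that paragraph.

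Section 6.5.3 gives the same two paths but a narrower release: "Participants undergoing LND will no longer need bilateral groin ultrasound and blood collections every two months and clinical examinations every three months". Section 7.5.2 repeats both the paths and this LND-only release.

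Elsewhere the schedule is binding:

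- Section 7.5.2, on the 3-monthly examinations: "This requirement persists for a duration of 12 months".
- Section 6.5.3: "Patients that fail to comply with the serial ultrasound and clinical examination schedule will be removed from the trial".
- Section 12.7, after a missed scan or examination: "Actions will be implemented to mitigate the risk, which may include the possibility of removing the patient from the trial".
- Section 12.1, describing the precaution against a groin recurrence that grows undetected: "participants in the intervention group will have a groin ultrasound scan every 2 months and a clinical examination every 3 months".

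**The concern.** Two rules cover the same woman. If she has an abnormal node, does not have LND and chooses to continue USM, sections 6.5.3 and 7.5.2 keep her on the mandatory schedule, while the last sentence of 10.6.5.1 takes her off it. A site cannot tell whether a missed scan in such a woman should be chased, should lead to removal from the trial, or needs no action.

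The women concerned have an abnormal, unresected node. Section 3.2 puts mortality above 90% within 12 months once missed positive nodes become enlarged and palpable, and section 12.1 names the 2-monthly scan and 3-monthly examination as the protection against this. Under the intention-to-treat principle in section 11.2 these women also stay in the USM arm, where the primary endpoint depends on palpable, histologically positive nodes being found by 12 months.

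**Working it through.** **Step 1: who is released, section by section.**

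| Place | Women addressed | Released from scans and examinations |
|---|---|---|
| 6.5.3 | USM women with an abnormal node or other concern | Only those undergoing LND |
| 7.5.2 | USM women with any concerning finding | Only those undergoing LND |
| 10.6.5.1, second-last paragraph | USM women with an abnormal node or other concern | No release stated; continuing USM is allowed |
| 10.6.5.1, last paragraph | USM women with an abnormal node | All of them, with no condition |

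The rules agree for women who have LND. They disagree for women who keep the node and continue USM, a path that the protocol provides for in all three sections.

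**Step 2: can the sentence be read as making the schedule optional?** That would still conflict with the 12-month examination requirement in 7.5.2, the removal rule in 6.5.3 and the missed-visit rule in 12.7. None of these exempts a woman who has an abnormal node and no LND.

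**Step 3: how much of the schedule is lifted.** The plan gives no figure to reproduce. The counts come from the study schedule in section 16, taking week 8 as month 2:

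- Postoperative USM scans: months 2, 4, 6, 8, 10, 12, so 6 in all.
- Interventional-arm physical examinations: months 2, 3, 6, 9, 12, so 5 in all.

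For an abnormal scan at month *t*, the share lifted is the number of visits scheduled after *t* divided by the total:

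| Abnormal scan at | Scans lifted | Examinations lifted |
|---|---|---|
| Week 8 | 5/6 = 83% | 4/5 = 80% |
| Month 4 | 4/6 = 67% | 3/5 = 60% |
| Month 6 | 3/6 = 50% | 2/5 = 40% |
| Month 8 | 2/6 = 33% | 2/5 = 40% |
| Month 10 | 1/6 = 17% | 1/5 = 20% |
| Month 12 | 0/6 | 0/5 |

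The longest period with no required groin scan or trial examination is 12 − 2 = about 10 months.

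**Step 4: what remains.** Disease status, adverse events, pain, quality of life and lymphoedema are still collected to 12 months. Sections 7.5.3 to 7.5.5, 7.5.7 and 7.5.8 allow the contacts at months 4, 6, 8, 10 and 12 to take place by telephone or post, and such a contact cannot replace palpation or ultrasound of the groin.

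**The case against.** The strongest reply is that this is a dropped qualifier and not a second rule. Section 10.6.5.1 presents itself as restating 6.5.3, and its last paragraph has the same two parts as the LND text in 6.5.3 and 7.5.2: data collection continues, and scans, examinations and bloods stop. Section 7.5 says that a change to suspicious triggers action such as LND. A careful reader of the whole protocol would reach the LND-only rule.

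It can also be said that the sentence ends a requirement without forbidding anything. A woman who opts to continue USM has chosen a course defined by 2-monthly scans and 3-monthly examinations. She must be referred to a clinician, and section 7.5 has USM women seen every 3 months as routine. The percentages therefore count requirements and not lost scans, and no effect on any analysis is shown.

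Much of this stands. The intent was probably LND only, other safeguards exist, and the figures describe a literal reading. What does not follow is that the text is sound. The preceding paragraph rules out assuming that every such woman has LND. Sections 7.5 and 12.1 make no exception for women with abnormal nodes, so they too conflict with the sentence. Site staff who turn to the section on positive nodes will find the wrong rule there.

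**Conclusion.** The concern holds. The last sentence of 10.6.5.1 is wrong as written for women who keep an abnormal node and continue USM. It contradicts 6.5.3, 7.5.2 and the paragraph just above it. Followed literally, it lifts the requirement for up to 5 of 6 scans and 4 of 5 examinations, with up to about 10 months of no mandatory groin surveillance.

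This size assumes that the sentence is applied as worded and that the section 16 schedule holds. Women who have LND are unaffected. The protocol does not say how many women would keep a node, so neither the number affected nor any change in P(recur|USM) can be given. It is an operational safety contradiction. The sample size, stopping boundaries and planned analyses are not affected.

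**What to change.** Replace the last sentence of 10.6.5.1 with wording such as: *For participants who undergo LND, the 2-monthly ultrasound, 3-monthly physical examination and blood tests are no longer required. Participants who continue groin USM remain on the 2-monthly ultrasound and 3-monthly examination schedule.*

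The cost is one reworded sentence. No other section, visit, sample size or analysis changes, and 10.6.5.1 then agrees with 6.5.3, 7.5.2 and 12.1.
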